## **5.2 Study Outcomes and Methods of Assessment:**

### **Primary Outcome**

- The proportion of participants who, at week 12, according to the investigator's assessment on the GAIS score, have achieved a score of 1 or higher (improved, much improved, or very much improved).

### **Secondary Outcome(s)**

- The proportion of participants who, at week 6 based on the investigator's assessment on the GAIS score, have achieved a score of 1 or higher (improved, much improved, or very much improved).
- Changes from baseline in waist circumference at weeks 6 and 12 using a flexible measuring tape.
- Changes from baseline in body weight at weeks 6 and 12.
- Changes from baseline in right and left thigh circumference at weeks 6 and 12 using a flexible measuring tape.
- Changes from baseline in flank fat on each side measured by caliper at weeks 6 and 12.
- Assessment of the trend in dermal and hypodermal thickness changes on both sides by measurement with ultrasonography from baseline to weeks 6 and 12
- Assessment of participant satisfaction at weeks 6 and 12
- Assessment of the incidence of AEs following treatment

### 5.3 Study Schedule Table

	Study Duration			
	Screening	Intervention	Follow-up	
Time Point	Screening Visit	Visit 1	Visit 2	Visit 3
Time	Day -7 to -1	Day 0	Week 6 ± 1 week	Week 12 ± 1 week
Informed Consent Form	×			
Assessment of Inclusion and Exclusion Criteria	×			
Medical History	×			
Physical Examination and Vital Signs		×	×	
Concomitant Medications	×	×	×	×
Skin Ultrasonography	×		×	×
Photography		×*	×	×
Intervention		×	×**	
GAIS Assessment			×	×
Assessment of Participant Satisfaction				×
Adverse Event Assessment	×	×	×	×

\* Photography must be performed prior to injection.

\*\* In case a touch-up injection is deemed necessary by the physician.

## **6 Sample Size Calculation Method**

In this study, 30 participants will be enrolled.

### **6.1 Statistical Analysis**

#### **Study Profile**

All participants who sign the informed consent form will be included in the final statistical report. The participants flow throughout the study, reasons for withdrawal from the study, and major deviations and violations of the protocol will be reported.

#### **Primary Endpoint Analysis**

Participants who, in the GAIS score assessment by the investigator, received a score of 1 or higher will be reported with the number and percentage.

#### **Secondary Endpoint Analysis**

Descriptive analysis of data for quantitative variables will be reported as mean and standard deviation (SD) or median and interquartile range (IQR), based on the data distribution, and for qualitative variables as the number and percentage. Changes over time will be analyzed using repeated measures analysis of variance (repeated measures ANOVA) or the Friedman test, depending on the data distribution. Comparisons between baseline and subsequent timepoints will also be performed using the paired t-test or the Wilcoxon test, as appropriate. The significance level for the tests will be considered as 0.05.

#### **Adverse Events' Analysis**

AEs will be classified according to the MedDRA dictionary based on the Preferred Term (PT) and analyzed in terms of frequency and percentage. The severity and seriousness of each event will also be reported.

## **7 Harms**

#### **Adverse Events**

An AE is described as any occurrence that happens to a participant in the study and presents with clinical manifestations differing from the progression of baseline conditions. It does not necessarily have a causal relationship with the investigational treatment used in the study.

Clinical manifestations that will be reported as AEs include any symptom, sign (such as an abnormal laboratory result), or temporary illness associated with the use of the investigational product, regardless of whether a causal relationship with the product is suspected or not.

An adverse drug reaction (ADR) is described as a harmful response to a drug that occurs at doses normally used in humans for the prevention, diagnosis and treatment of diseases, or modification of a physiological function.

### **Classification of AEs Based on Severity**

The severity of AEs is classified by the physician's assessment as mild, moderate, or severe.

### **Classification of AEs Based on Seriousness**

An event is considered a serious adverse event (SAE) if:

- Results in death.
- Is life-threatening or results in a risk of death.
- Requires inpatient hospitalization or prolongation of existing hospitalization.
- Results in persistent or significant disability/incapacity.
- Is a congenital anomaly/birth defect.
- Results in a condition requiring special clinical intervention for the participant.

### **Adverse Event Reporting**

All AEs, including both serious and non-serious AEs that occur following administration of the product, shall be precisely documented. The description of the event, its chronological sequence relative to the time of product administration, its duration, the processes utilized for its diagnosis, and the outcomes of any re-exposure to the product must be recorded. Furthermore, a qualitative assessment of the AE, conducted by the investigator based on its severity and its relationship to the administered product, must also be documented.

## **8 Ethical Considerations and Dissemination of Results**

### **8.1 Ethics Committee Approval**

- Ethics committee approval is mandatory prior to the initiation of this study.
- No participants will be enrolled in the study without providing informed consent.
- All participants will be informed that they may withdraw from the study at any time and without providing any explanation, should they so wish.
- AE report forms will be evaluated during the study. The study research team is responsible for the prompt review of any AE that occur (regardless of whether the event is directly attributable to the investigational drug or not).

## **8.2 Informed Consent Form**

During the screening of participants for study enrollment and prior to any procedures, the investigator shall fully explain the purpose and details of the study to the participants in clear and simple language. After answering any potential questions, sufficient time and opportunity will be provided to the participants to inquire about the study details so that they can decide whether or not to participate in the study. Additionally, the study investigator will explain to the participants that they are free to refuse the use of their information or to withdraw from the study at any time and for any reason.

When the information provided to the participants has been understood by them and the requested explanations have been given to the participants, the participants is given sufficient time to sign the informed consent form and to write their first and last name on the consent form. The investigator physician shall also stamp and sign the relevant consent form. For each participants, two copies of the consent form, stamped and signed by both the physician and the participants, are prepared; one copy is given to the participants and the other copy remains at the site and with the investigator. The investigator and the study sponsor may, at any time and for operational reasons, withdraw the participants from the study. Any other necessary information to fully protect the human rights of the participants, in accordance with GCP guidelines, local and national regulations for conducting clinical studies, and the Declaration of Helsinki, will also be explained.

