17. Medical and/or psychiatric conditions of such severity that they may interfere with the outcomes of the study
18. Having a known bleeding disorder or the use of medications that increase the likelihood of bleeding after injection
19. Presence of hair in the flank area that interferes with assessment or treatment
20. Predisposition to hypertrophic scar formation
21. History of anaphylaxis or allergy to lidocaine (or other amide anesthetics), hyaluronic acid products, or streptococcal proteins
22. Affliction with Porphyria
23. Presence of active inflammation, infection, malignant or premalignant lesion, or non-healed ulcer in the flank region

24. Having a condition or being in a situation which, in the opinion of the investigator, may place the individual at significant risk, disrupt the study results, or interfere with the individual's participation in the study.

- **Withdrawal Criteria:**

1. Withdrawal of participant from informed consent
2. Non-compliance, including refusal to adhere to the medical requirements of the study, failure to undergo procedures specified in the study protocol, or use of prohibited medications.
3. Inability to follow up on the participant's status
4. Treatment of the flank area with hyaluronic acid fillers or semi-permanent fillers during the course of the study
5. The use of any permanent filler or silicone materials in the flank area during the course of the study
6. Undergoing any cosmetic procedures in the treatment area during the study period (such as surgery)
7. Having conditions that, in the opinion of the investigator, may interfere with the assessment of efficacy

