	
17. Medical and/or psychiatric problems that are severe enough to interfere with the study results18. Known bleeding disorder or receiving medication that will likely increase the risk of bleeding after injection19. Having hair that would interfere with evaluation and treatment of the flank area20. Being prone to develop hypertrophic scarring21. Having a history of anaphylaxis or allergy to lidocaine (or any amide-based anesthetics), hyaluronic acid products, or Streptococcal protein22. Having porphyria23. Having an active inflammation, infection, cancerous or precancerous lesion, or unhealed wound in the flank area24. Having a condition or being in a situation that, in the investigator's opinion, may put the subject at significant risk, may confound the study results, or may interfere significantly with the subject's participation in the study
Randomization	The subjects will not be randomly allocated because the study is single arm and all subjects will receive Embella.
Blinding	This study is open-label and there is no blinding in this study
Intervention	Deoxycholic acid, SC, 0.15 ml each injection, up to 2-4 ml in each site (2 ml at visit 1 for everyone, and 2 ml at visit 2 unless the patient does not agree)
Efficacy and Safety outcomes	
Primary endpoint:
 
The proportion of participants with grade 1 or higher (“improved, much improved, very much improved”) in investigator-assessed Global Aesthetic Improvement Scale (GAIS) at Week 12
 
Secondary endpoints:
 
Secondary endpoints:
 
1. Safety assessment by evaluation of adverse events (AEs)2. The proportion of participants with grade 1 or higher (“improved, much improved, very much improved”) in

	
investigator-assessed Global Aesthetic Improvement Scale (GAIS) at Week 6
 
3. Change from Baseline in ultrasonographic measurement of dermal and hypodermal thickness on both flanks at weeks 6 and 124. Changes from Baseline in the bodyweight (Kg) at Weeks 6 and 125. Changes from Baseline in right and left thigh circumference at Weeks 6 and 12 using a flexible tape measure6. Changes from Baseline in caliper measurement (mm) of flank fat on each side at Weeks 6 and 127. Changes from Baseline in waist circumference at Weeks 6 and 12 using a flexible tape measure8. Subject's satisfaction at Weeks 6 and 12 using a 10-point Likert scale

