Statistical Plan	
The data analysis procedure will cover the cleaning, inspecting, and transforming process. Also, the descriptive analysis will be performed using frequency and percentage, mean and standard deviation (SD) or median and interquartile range (IQR) regarding the type of the variables.
 
Primary Endpoint:
 
The primary effectiveness endpoint will be reported as the number and percentage of participants with a ≥ 1-point improvement from baseline in the investigator's GAIS at week 12
 
Secondary Endpoints:
 
The secondary effectiveness endpoints will be reported as the number and percentage of participants with a ≥ 1-point improvement from baseline in the investigator's GAIS and the subject's GAIS at week 6, the number and percentage of participants with a ≥ 1-point improvement from baseline in the subject's GAIS at week 12, the number and percentage of patient satisfaction status at week 12 and mean and SD or median and IQR of patient satisfaction score and changes in derma and hypoderm thickness at weeks 6 and 12 compared to baseline.

	
Safety:
 
The safety data will be analyzed primarily using incidence and frequency. Adverse events' severity, seriousness, and causality assessment will be reported.

Withdrawal Criteria	
1. Withdrawal of consent by the patient2. Noncompliance, including refusal of study medical requirements, refusal of procedures as stated in the study protocol, or use of prohibited medications3. Not possible to follow the patient's condition (loss to follow-up)4. Treatment to the flanks with hyaluronic acid fillers or semi-permanent filler throughout the study5. Use of any permanent filler materials or silicone in the flanks throughout the study6. Performing any cosmetic procedure in the treatment area during the study period (i.e., surgery)7. Having a condition that, in the investigator's opinion, may interfere with the efficacy assessment

Study Timeline

	Study Duration			
	Screening	Intervention	Follow-up	
Time Point	Screening Visit	Visit 1	Visit 2	Visit 3
Time	Day -7 to -1	Day 0	Week 6 ± 1 week	Week 12 ± 1 week
Informed Consent Form	×			
Assessment of Inclusion and Exclusion Criteria	×			
Medical History	×			
Physical Examination and Vital Signs		×	×	
Concomitant Medications	×	×	×	×
Skin Ultrasonography	×		×	×
Photography		**	×	×
Intervention		×	**	
GAIS Assessment			×	×
Assessment of Participant Satisfaction				×
Adverse Event Assessment	×	×	×	×

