No imputation will be done.

Outlier data

Outliers are identified by examining standard charts, and those that are visually "distinct" are evaluated to check the impact on the results by comparing the results of the analysis with and without outliers.

Data Transformations

No transformations of raw data are planned prior to statistical analysis. All variables will be analyzed using their original measurement scales, unless transformation is deemed necessary during model diagnostics. In such cases, justification and details will be documented in the statistical outputs and Clinical Study Report (CSR).

Multiple comparisons and multiplicity

No formal procedures for multiplicity adjustment are planned for this study, as the study was not designed to perform multiple statistical comparisons for primary or key secondary endpoints. Therefore, the overall Type I error rate will not be adjusted.

Primary Endpoint Analysis

Participants who, in the GAIS score assessment by the investigator, received a score of 1 or higher will be reported with the number and percentage.

Secondary Endpoint Analysis

Descriptive analysis of data for quantitative variables will be reported as mean and standard deviation (SD) or median and interquartile range (IQR), based on the data distribution, and for qualitative variables as the number and percentage. Changes over time will be analyzed using repeated measures analysis of variance (repeated measures ANOVA) or the Friedman test, depending on the data distribution. Comparisons between baseline and subsequent timepoints will also be performed using the paired t-test or the Wilcoxon test, as appropriate. The significance level for the tests will be considered as 0.05.

Adverse Events' Analysis

AEs will be classified according to the MedDRA dictionary based on the Preferred Term (PT) and analyzed in terms of frequency and percentage. The severity and seriousness of each event will also be reported.

Methods used for assumptions to be checked for statistical methods

For t-test, normality of distributions will be assessed using the Shapiro-Wilk test.

References

2. Garibyan L, Sipprell WH, Jalian HR, Sakamoto FH, Avram M, Anderson RR. Three-dimensional

volumetric quantification of fat loss following cryolipolysis. *Lasers Surg Med.* 2014;46(2):75–80.

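### Withdrawals initiated by the investigator or sponsor, on undefined operational grounds or on the opinion of the role that rates the unblinded primary GAIS, could leave week-12 scores missing for outcome-related reasons

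*Protocol*

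**What the plan says.** **Routes out of the study.** Protocol 5.1 lists seven withdrawal criteria, and the SAP repeats them in its synopsis and in Section 3. The seventh, in the protocol's words, is "Having conditions that, in the opinion of the investigator, may interfere with the assessment of efficacy". Protocol 8.2, in describing the consent process, adds a further route: "The investigator and the study sponsor may, at any time and for operational reasons, withdraw the participants from the study". It does not say what counts as operational, and the SAP does not mention this route.

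**Who rates the endpoint.** The primary outcome in protocol 5.2 is "The proportion of participants who, at week 12, according to the investigator's assessment on the GAIS score", with a score of 1 or more counted as response. The same role rates a secondary outcome "at week 6 based on the investigator's assessment on the GAIS score". The SAP synopsis says: "This study is open-label and there is no blinding in this study".

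**What happens to a missing score.** The SAP's missing-data rule is one sentence: "No imputation will be done". The primary endpoint analysis in both documents is a number and a percentage, with no denominator named. Both documents put everyone who consents into the final report and promise to report participant flow and reasons for withdrawal (Study Profile). Neither separates stopping treatment from ending follow-up, and neither says that a withdrawn participant is still assessed at week 12.

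**The concern.** In a single-arm trial the responder percentage is the whole primary result. No comparator would share a bias in who gets scored. The role that produces the score can also take a participant out before the score is due, knowing the week-6 score and without masking. The sponsor has a similar power on grounds that nobody has defined. If those taken out tend to be those doing less well, the missing scores are related to outcome. A plan with no imputation, no non-responder rule and no stated denominator has nothing to correct for that.

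This differs from participants who leave by choice or are lost to contact. There, data may be unobtainable. Here, the study team decides to stop collecting data that it could still collect.

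**Working it through.** The plan states no expected response rate, dropout rate or power, so there is no figure of its own to reproduce. The check is in two parts.

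**1. Do the rules permit outcome-related missing scores?**

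- Removal by the team: permitted by protocol 8.2 (operational, undefined) and by criterion 7 (investigator opinion).
- Knowledge of response at that time: available, because GAIS is rated at week 6 and the study is open-label. The week-6 score informs the week-12 result but does not fix it, since a second injection may be given at that visit.
- Assessment after removal: not provided for in either document.
- Replacement of the missing score: none.

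So the route exists. Whether it would be used cannot be learned from the documents.

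**2. How far could the primary percentage move?**

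Input from the documents: 30 participants (protocol section 6). Assumptions: all 30 are treated, *r* respond, and *w* withdrawn participants would all have been non-responders at week 12.

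- Scored participants only: r / (30 − w)
- All 30, withdrawn counted as non-responders: r / 30
- Difference: r·w / [30 × (30 − w)]

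| r | All 30 | w = 1 | w = 2 | w = 3 | Shift at w = 3 (points) |
|---|---|---|---|---|---|
| 15 | 50.0% | 51.7% | 53.6% | 55.6% | 5.6 |
| 18 | 60.0% | 62.1% | 64.3% | 66.7% | 6.7 |
| 21 | 70.0% | 72.4% | 75.0% | 77.8% | 7.8 |
| 24 | 80.0% | 82.8% | 85.7% | 88.9% | 8.9 |

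For example, with r = 18 and w = 3 the shift is 18 × 3 / (30 × 27) = 54/810 = 6.7 points. The exact (Clopper-Pearson) 95% interval moves from 40.6–77.3% for 18/30 to 46.0–83.5% for 18/27.

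Against sampling error, SE = √[p(1 − p)/30] is 8.9 points at 60% and 8.4 points at 70%. Three removals therefore shift the estimate by 6.7/8.9 = 0.75 and 7.8/8.4 = 0.93 of a standard error.

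**3. Dependence on the assumptions.** With all 30 in the denominator and withdrawn participants counted as non-responders, the percentage stays at r/30 whatever *w* is. If the three withdrawn participants would instead have responded, the full result behind an observed 18/27 would be 21/30 = 70.0%, and the observed 66.7% would be too low. The direction therefore depends on who is withdrawn, and only a week-12 assessment settles it.

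**The case against.** The strongest reply is that nothing here shows selective removal. The 8.2 sentence sits among the points to be explained at consent, is limited by its words to operational grounds, and can be read as needing investigator and sponsor together. Criterion 7 requires a condition that interferes with assessment, and non-response is not such a condition. The documents name a role, not a person, so it is an inference that one individual both rates and withdraws. The upward shift also needs an observed-case denominator. All of this stands, and it limits the point to what the rules permit. It does not supply a week-12 score or a denominator: inclusion in the final report is not a definition of the primary percentage.

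A reader might infer more than the documents support:

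- *That 8.2 contradicts a closed list.* The seven criteria are never called exhaustive, so 8.2 adds a ground.
- *That criterion 6 conflicts between texts.* The protocol has "Undergoing any cosmetic procedures in the treatment area during the study period (such as surgery" and the SAP synopsis has "Performing any cosmetic procedure in the treatment area during the study period (i.e., surgery". Both cover any cosmetic procedure in the area. Only the parenthesis differs, and participants must in any case agree to abstain from other flank treatments.
- *That injection reactions would be used as criterion 7 conditions, or that AE follow-up is cut short in those most harmed.* No text treats a reaction in this way, and protocol section 7 requires all AEs after administration to be documented.
- *That selective removal would be invisible.* Week-6 GAIS, photographs and ultrasonography are scheduled, and withdrawal reasons are reported. A cluster of week-6 non-responders among the withdrawn could be seen; what would be missing is their week-12 score.

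**Conclusion.** The point holds as a gap in the design. Two discretionary withdrawal routes are open to the study team, one of them to the role that rates the unblinded primary endpoint with week-6 results in hand, and nothing secures the week-12 score afterwards. It does not hold as evidence of bias in this trial.

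Its possible size is moderate. Three removed non-responders out of 30 would add 5.6 to 8.9 points for underlying rates of 50% to 80%, which is less than one standard error in the 60% and 70% cases worked above. This rests on three assumptions: an observed-case denominator, all those removed being non-responders, and all 30 being treated. Without the first, under a non-responder rule, the shift is zero. Because the route can be closed cheaply, it should be closed.

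**What to change.** 1. In protocol 8.2, limit the operational-grounds sentence to closure of the study or site, or remove it for individual participants.
2. In protocol 5.1 and both SAP lists, state that criteria 4 to 7 are recorded as protocol deviations or intercurrent events and do not end data collection. The week-12 GAIS, outcome measurements and AE assessment are still done unless consent is withdrawn or contact is lost. Whether any further injection is given is a clinical matter outside this point.
3. In the SAP's primary endpoint analysis, report the proportion over all treated participants, with those lacking a week-12 score counted as non-responders, at least as a sensitivity analysis beside the observed-case figure. How to score a participant who had another flank procedure but was assessed at week 12 is a choice of estimand for the study team to make and state.
4. List each withdrawal with its date, who decided it and the latest GAIS.

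The cost is a wording amendment to two protocol sections and the SAP, one extra table and one listing. The week-12 visits are already scheduled. The downside is a few noisier week-12 assessments and a responder rate that may be slightly less favourable.
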